2.2 STUDY OBJECTIVES

Primary Objective: *To estimate and compare the incidence rates of venous thromboembolism (VTE) among women receiving BZA and women receiving a bisphosphonate for treatment of osteoporosis.*

Secondary Objective 1: *To estimate and compare the incidence rates of VTE among women receiving bazedoxifene and women receiving raloxifene for treatment of osteoporosis.*

Secondary Objective 2: *To estimate and compare the incidence rates of selected clinical endpoints (listed as secondary endpoints in “section 6 Endpoints and Covariates”) among women receiving bazedoxifene and women receiving a bisphosphonate for treatment of osteoporosis.*

Secondary Objective 3: *To estimate and compare the incidence rates of selected clinical endpoints (listed as secondary endpoints in “section 6 Endpoints and Covariates”) among women receiving bazedoxifene and women receiving raloxifene for treatment of osteoporosis.*

3 INTERIM ANALYSES AND FINAL REPORT

An interim analysis will be conducted once, after four years of study data become available. This interim analysis will include a calculation of crude event rates for the study outcomes in each exposure group. The observed rates of the primary endpoint will be used to determine if the rates are sufficient to continue the study as planned. Based on the results of this interim analysis, the study may be extended in order to accrue the number of events required to preserve the precision of the incidence rate ratios (as defined in the study protocol section 7.1, Sample size calculation). There will be no other changes in the study design nor will there be any changes needed to the originally planned analysis as a result of this interim analysis.

Final analysis will be conducted within 12 months of the end of the study.

4 HYPOTHESES AND DECISION RULES

4.1 STATISTICAL HYPOTHESES

Risk of the primary and secondary endpoints in each treatment cohort is equivalent:

- H_0 : Hazard_{bazedoxifene} = Hazard_{bisphosphonate} (Hazard Ratio [HR]=1)
- H_0 : Hazard_{bazedoxifene} = Hazard_{raloxifene} (HR=1)

That is, the null hypotheses will be that the rates of the primary endpoints events are the same in patients treated with BZA as in patients treated with bisphosphonate (or raloxifene). The null hypothesis for the analysis of each endpoint will be HR=1; the alternative hypothesis will be HR \neq 1.

4.2 STATISTICAL DECISION RULES

Incidence rates of the primary and secondary endpoints will be calculated with a 95% Confidence interval (CI). The HR from Cox proportional hazard regression models will be used for comparison of event rates of the primary and secondary endpoints in each exposure (treatment) cohort. Statistical two-sided tests will be used with a significance level of 0.05.

Multiple Comparisons/ Multiplicity

No adjustments for multiple comparisons or multiplicity are planned among endpoints for this Post Authorization Safety Study.

5 ANALYSIS SETS/ POPULATIONS

5.1 FULL ANALYSIS SET

There is no active de novo patient enrolment in this study and all women in the database who meet the inclusion criteria during the enrolment period will be included in the full analysis set.

5.2 SAFETY ANALYSIS SET

The safety analysis set is the same as the full analysis set.

5.3 OTHER ANALYSIS SET

Not Applicable

5.4 SUBGROUPS

Age stratified randomly selected subgroup

In the current dataset, there are 1,823 patients in the bazedoxifene group and 82,041 patients in the bisphosphonate group. This means that there is more than 40 times the number of subjects in the bisphosphonate group compared to the number of subjects in the bazedoxifene group. To limit the number of patients in the bisphosphonate group, an age stratified random subgroup will be selected. Based on the sample size and relative risk estimates provided in the final study protocol (study protocol section 7.1, Sample size calculation), the 1,823 bazedoxifene subjects will be adequately matched by a ratio of 1:6 bisphosphonate subjects. Therefore $1,823 \times 6 = 10,938$ bisphosphonate treated subjects are needed to be randomly selected from the total of 82,041 bisphosphonate treated subjects.

Selection scheme: The age of subjects in the study will be categorized into 4 groups (45-49, 50-59, 60-69, and ≥ 70). In the bisphosphonate group, the percentage of subjects in each of these age groups is 1.4%, 13.7%, 28.7%, and 56.2% respectively. To maintain the same proportion of subjects in each age group for the bisphosphonate subgroup, there will be $1.4\% \times 10,938 = 153$ bisphosphonate treated subjects randomly selected from the 45-49 age group; $13.7\% \times 10,938 = 1,499$ subjects randomly selected from the 50-59 age group; $28.7\% \times 10,938 = 3,139$ subjects randomly selected from the 60-69 age group; $56.2\% \times 10,938 = 6,147$ subjects randomly selected from ≥ 70 age group.

Incident cases of study endpoints

Women with a history of study end points recorded prior to the index prescription will not be included in the analysis for that specific outcome, but will be analyzed separately as subgroups for each study end point. The analyses of the primary and secondary endpoints will be performed using these incident cases of study endpoints subgroups.

For example, a woman with a history of VTE period prior to the index prescription will be categorized as a prevalent case and will be excluded from the primary VTE analysis. A separate analysis for subgroup of women with a medical history of VTE will be performed and the woman would remain eligible for the analysis of other outcomes as normal. Depending on the number of patients in these subgroups of prevalent cases of each endpoint, this supplemental analysis is likely to have low power to perform any statistical comparison and will be descriptive in nature.

Incident/new user subgroup

In this subgroup analysis, cohorts of incident and not prevalent users of bisphosphonate and raloxifene will be compared to a cohort of incident BZA users. Patients will be defined as incident/new user if they have not had any treatment for osteoporosis in at least 6 months prior to the index date. The index date for each patient is the date of the first recorded prescription for BZA or bisphosphonate or raloxifene during the study enrolment/accrual period.

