#### **4. STUDY POPULATION**

All women in the Cegedim database meeting the inclusion criteria will be included in the analysis without any sampling process.

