## 6.3. Endpoint identification

The relevant diagnostic codes for each of the endpoints will be specified in the statistical analytic plan. Endpoints will be identified based on an electronic search for the relevant diagnostic codes in the diagnosis fields of the medical records during the follow up period.

For the identified potential cases, the electronic medical record will be retrieved and reviewed by a clinical expert to confirm the diagnosis for the following endpoints:

The primary endpoint:

- a. Venous thromboembolism (VTE) defined as deep vein thrombosis (DVT), pulmonary embolism (PE), retinal vein thrombosis, and sinus thrombosis.

Secondary endpoints

- b. Ischemic stroke
- c. Thrombotic and ischemic cardiac disorders (including myocardial infarction, myocardial ischemia, and coronary occlusion; and includes both acute and chronic disorders).
- d. Malignancies: Breast, ovarian, renal, thyroid and endometrial.
- e. Any ocular event with a vascular etiology (possibly indicative of retinal vein thrombosis, e.g. retinal arterial thrombosis, retinal hemorrhage, visual field defects of vascular origin).

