## 7. DATA ANALYSIS/STATISTICAL METHODS

The details of the data analysis will be documented in a Statistical Analysis Plan (SAP) document, which will be maintained by the sponsor. The SAP will elaborate, and may modify the analytic plans outlined in the protocol; however, any major modifications will be reflected in a protocol amendment.

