### 7.1. Sample Size Calculation

There is no active de novo patient enrollment in this study and all women in the database who meet the inclusion criteria during the recruitment period will be included in the analysis. Therefore, the focus of the sample size calculation was to determine the precision of the estimated incidence rate ratios (IRR) that can potentially be achieved in the study depending on several different hypothetical scenarios of subject accrual. Depending on drug uptake in the participating countries, speed of accrual, event rates, and actual dropout rates, the precision of the estimated incidence rate ratio may change.

The estimates are based on the expected incidence rate of VTE as the primary endpoint. It is estimated that the incidence rate of VTE in women who are not treated with a SERM or HT is 1.74/1000 patient-years (PY), based on data from the placebo groups in bazedoxifene clinical trials. It is assumed that women treated with raloxifene would have a higher incidence of VTE, of 2.17/1000 PY, based on data from the Phase III pivotal trials of bazedoxifene. The rate of VTE observed in the raloxifene arm of the bazedoxifene pivotal trials is lower than the rate reported in the Multiple Outcomes of Raloxifene Evaluation (MORE) trial [1]. In the MORE trial, the incidence rate of VTE was 3.5/1000 patient-years in women randomized to raloxifene. Therefore, our calculations are likely to be substantially more conservative than estimates based on rates in the literature.

All estimates (Table 3, Table 4) were calculated with two-sided 95% confidence intervals. According to the study plan, there will be a 3-year accrual period and each woman will be followed for up to 5 years from enrollment. Since osteoporosis therapies are chronic therapies, it is likely that women will be exposed to the drugs for more than one year. A conservative annual loss to follow up rate of 15% was used in the estimation. Estimates were based on Wald 95% confidence intervals [2]

**Table 3: 95% Confidence Intervals (CI) for Incidence Rate Ratios (IRR) with different numbers of patients in the BZA arm and the primary comparator arm**

Bazedoxifene (n)	Bisphosphonate (n)	BZA:Bisphosphonate	Underlying Incidence Rate Ratio (IRR)		
			1	1.5	2
			95% CI of observed point estimate of IRR		
2150	8600	1:4	0.6, 1.7	1.0, 2.4	1.3, 3.0
2000	8000	1:4	0.6, 1.8	0.9, 2.4	1.3, 3.1
1750	10,500	1:6	0.6, 1.8	0.9, 2.5	1.3, 3.1
1500	12,000	1:8	0.5, 1.9	0.9, 2.5	1.3, 3.2

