8.2.5 SUMMARY OF STATISTICAL ANALYSIS

Analyses for Primary Objective and Secondary Objective 1

Comparator: BZA vs. bisphosphonate (primary objective), BZA vs. raloxifene (secondary objective 1).

Study endpoint: VTE.

Populations: a. Full BZA full raloxifene, random age stratified bisphosphonate subgroup
b. Incident user subgroup.

Statistical Method:

- i. Incidence rate, cumulative method (*Total new cases during follow-up period / Total persons at risk during follow-up period*) with stratification by risks of interest e.g. Age, BMI.
- ii. Univariate and multivariate incidence rate by incidence density (*Total new cases during follow up period / Total person years during follow-up period*)*1000) method using Cox regression model and a Likelihood Ratio Test for testing Hazard Ratio (HR) =1 (ratio of hazard in BZA population vs. bisphosphonate/raloxifene population) with covariates associated with VTE outcome and exposure (Drug groups).

Sensitivity analyses:

- i. Repeat analysis will be conducted that compares using a 30-day and a 90-day definition of recent exposure with using the 60-day definition.
- ii. Missing Data: First, the analyses will be repeated utilizing a complete dataset in which cases with missing values of main study covariates of BMI, smoking status and alcohol status have been deleted. Second, multiple imputation for the missing values of BMI, smoking status, alcohol status will be used in the second set of analyses.

Multiple imputation procedure:

- 1) Estimate distribution of BMI, smoking status and alcohol status according to patients whose data are available.
- 2) For the patients who had missing values those variables draw values of the variables from the distribution from 1).
- 3) With the imputed dataset (including none-missing data), estimate HR as described.
- 4) Repeat 2)-3) for m times, and record HR of each time.
- 5) Calculate mean of m estimates of HR.
- 6) Adjust variance of HR with the following formula, and use the variance to calculate confidence interval.

$$V = \left(1 + \frac{1}{M}\right) V_B + V_W.$$

V_B is the between imputation variance, and V_W is within imputation variance.

Analyses for Secondary Objective 2 and Secondary Objective 3

Comparator: BZA vs. bisphosphonate (secondary objective 2), BZA vs. raloxifene (secondary objective 3).

Study endpoint: Secondary endpoints.

Population: a. Full BZA, full raloxifene, random age stratified bisphosphonate subgroup.
b. Incident user subgroup

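### The SAP compares bazedoxifene with a random 13% of the bisphosphonate cohort, although the protocol rules out sampling; this gives up 12–22% of the information at rate ratios of 1 to 2

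*SAP*

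**What the plan says.** Three places put every eligible woman in the analysis:

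- Protocol section 4: "All women in the Cegedim database meeting the inclusion criteria will be included in the analysis without any sampling process".
- Protocol 7.1: "all women in the database who meet the inclusion criteria during the recruitment period will be included in the analysis".
- SAP 5.1: "all women in the database who meet the inclusion criteria during the enrolment period will be included in the full analysis set".

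SAP 5.4 then reports that "there are 1,823 patients in the bazedoxifene group and 82,041 patients in the bisphosphonate group" and continues: "To limit the number of patients in the bisphosphonate group, an age stratified random subgroup will be selected". It cites protocol 7.1 to support a 1:6 ratio, takes 1,823 × 6 = 10,938, and divides that number over four age bands in the bisphosphonate group's own proportions.

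SAP 8.2.5 defines population (a) for the primary objective and secondary objective 1 as "Full BZA full raloxifene, random age stratified bisphosphonate subgroup". It uses the same definition for secondary objectives 2 and 3. It lists no analysis of all 82,041 women. Population (b), incident users, is not said to be sampled.

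Protocol section 7 lets the SAP modify the analysis, but adds that "any major modifications will be reflected in a protocol amendment".

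**The concern.** The protocol and the SAP specify different comparator populations for population (a), which includes the primary bazedoxifene–bisphosphonate comparison. A reader of the protocol would expect 82,041 comparators. A programmer following SAP 8.2.5 would use 10,938 and leave out 71,103. The SAP does not say that it departs from protocol section 4, and its only reasons are a wish to limit numbers and the adequacy of 1:6.

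The sampled analysis must also be less precise than one on data already held. Bazedoxifene accrual was low enough for SAP 2.1 to record an extended accrual period, so extra precision from the comparator arm has some value. The relative loss grows with the true rate ratio, so it is largest when there is a harm to detect.

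**Working it through.** **Inputs.** Bazedoxifene n₁ = 1,823; bisphosphonate n₀ = 10,938 (sample) or 82,041 (all), from SAP 5.4. Comparator VTE rate r = 1.74 per 1,000 person-years, rate ratios 1, 1.5 and 2, Wald 95% limits, up to 5 years of follow-up and 15% annual loss, from protocol 7.1. Two-sided 0.05 level, from SAP 4.2.

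**Sample size.** 1,823 × 6 = 10,938, which is 13.3% of 82,041. The strata 153 + 1,499 + 3,139 + 6,147 also add to 10,938. The full ratio is 82,041 / 1,823 = 45 to 1.

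**Reproducing protocol Table 3.** With T mean person-years per woman,

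Var(log IRR) = 1/(IRR·r·T·n₁) + 1/(r·T·n₀), limits = IRR·exp(±1.96·SE).

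The protocol does not state T. T = 5 × 0.85 = 4.25 reproduces 22 of the 24 limits to one decimal, including all six in the 1:6 row. The two misses are in the 2,150:8,600 row (0.94 against 1.0, and 3.06 against 3.0). Compounding 15% loss each year gives T = (1 − 0.85⁵)/(−ln 0.85) = 3.42, which reproduces only 3 of 24. Both values are carried below.

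**Information lost.** r and T cancel if mean follow-up is equal in both arms:

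loss = 1 − [1/(1,823·IRR) + 1/82,041] / [1/(1,823·IRR) + 1/10,938].

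At IRR 2 this is 1 − (0.00027427 + 0.00001219)/(0.00027427 + 0.00009142) = 1 − 0.00028646/0.00036570 = 21.7%.

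| True IRR | Variance ratio, sample/all | Information lost | SE larger by |
|---|---|---|---|
| 1 | 1.141 | 12.4% | 6.8% |
| 1.5 | 1.210 | 17.3% | 10.0% |
| 2 | 1.277 | 21.7% | 13.0% |

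**Expected intervals at T = 4.25.** At IRR 2 the expected events are 1,823 × 4.25 × 0.00174 × 2 = 27.0 on bazedoxifene, against 80.9 (sample) or 606.7 (all) on bisphosphonate. SE = √(1/27.0 + 1/80.9) = 0.222 for the sample and √(1/27.0 + 1/606.7) = 0.197 for all.

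| True IRR | Sample | All women |
|---|---|---|
| 1 | 0.56–1.78 | 0.58–1.72 |
| 1.5 | 0.92–2.44 | 0.96–2.34 |
| 2 | 1.29–3.09 | 1.36–2.94 |

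At T = 3.42 and IRR 2 the SEs are 0.248 and 0.219, and the intervals are 1.23–3.25 and 1.30–3.07.

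**Power at IRR 2**, Φ(ln 2/SE − 1.96): 88% (sample) against 94% (all) at T = 4.25; 80% against 89% at T = 3.42. The protocol sets no power target, so these figures only compare the two designs.

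**Confounding.** The strata copy the bisphosphonate group's age distribution, not that of the bazedoxifene group. Sampling therefore neither creates nor reduces age imbalance between the arms.

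**The case against.** The strongest reply is that the planned precision is met. Protocol 7.1 plans for precision at ratios from 1:4 to 1:8, and 1,823:10,938 exceeds the 1,750:10,500 row of Table 3 in both arms. A random sample of a 45:1 comparator introduces no bias. No expected conclusion changes either: at a rate ratio of 2 both versions exclude 1, and at 1.5 both include it. All of this stands. It limits the point to a contradiction and an avoidable loss, but does not explain why the protocol's population was dropped.

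Workload is a fair argument. Protocol 6.3 says that for potential cases of the primary endpoint and several secondary endpoints "the electronic medical record will be retrieved and reviewed by a clinical expert to confirm the diagnosis". Using every comparator multiplies those reviews by about 82,041 / 10,938 = 7.5. SAP 5.4 does not give this reason, however, and it would not justify restricting code-based analyses.

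The scope also needs care:

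- SAP 5.4 calls the sample a subgroup, so the direct conflict is with the protocol. Against SAP 5.1, the point is that a full analysis set is defined but population (a) does not use it for bisphosphonates.
- SAP 8.1.4 starts the time-to-event analysis with newly prescribed patients, and population (b) is not said to be sampled. The loss is established for population (a) only.
- SAP 2.1 says more than 45% of patients lack a recorded osteoporosis diagnosis and leaves that criterion open. If only 55% of the bisphosphonate women qualified (45,122, an assumption) and bazedoxifene numbers were unchanged, the loss would be 10.8–18.9%.
- The documents give no country split of the 82,041, so the loss in the country-specific analyses cannot be computed.
- Whether the change counts as major under protocol section 7 is a judgement, and with pages removed from both documents the absence of an amendment cannot be proved.

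**Conclusion.** The concern holds. For population (a), SAP 5.4 and 8.2.5 sample where protocol section 4 says there will be no sampling, and the SAP does not acknowledge it. The cost is 12%, 17% and 22% of the information on the log rate ratio at true ratios of 1, 1.5 and 2, or standard errors 7%, 10% and 13% larger. This is moderate: intervals tighten modestly, and power at a ratio of 2 rises by 6 to 9 percentage points if all women are used.

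The percentages assume an unadjusted pooled analysis, equal mean follow-up in both arms, all 82,041 women eligible, and removal of prevalent VTE cases in the same proportion from each arm. They do not depend on the event rate or on T. The intervals and power do, and T = 4.25 is inferred from Table 3. The change should be made, but the sampled design does not fail the study's stated precision.

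**What to change.** In SAP 5.4 and in both population (a) lines of SAP 8.2.5, replace the random bisphosphonate subgroup with the full eligible bisphosphonate cohort for the code-based primary and secondary analyses. This restores agreement with protocol sections 4 and 7.1 and costs only SAP wording and computing time.

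If expert-review capacity is the real limit, say so and keep the random sample for record review only, while still reporting the code-based analysis on all women. Reviewing every comparator case would mean about 607 VTE records instead of 81 at T = 4.25 (488 instead of 65 at T = 3.42), plus about 7.5 times as many for each other endpoint reviewed under protocol 6.3. Keeping the sample for review avoids that work. In return, confirmed-case results keep the sample's lower precision and rest on a different comparator set from the code-based results, which the report should state.

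If the sponsor prefers to keep sampling throughout, protocol section 4 should be amended to say so, with the reason.

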8.1.2 INCIDENCE RATES

Incidence rates will be calculated for all endpoints in all cohort groups; incidence rate ratios and 95% confidence intervals will be calculated as specified previously.

The incidence rate for all end points will be calculated using both the cumulative incidence approach and an incidence density (person-time) approach. The cumulative incidence approach will be used as the primary analysis and it will be calculated as in the following formula:

$$\text{Incidence rate} = (\text{Total new cases during follow-up period} / \text{Total persons at risk during follow-up period})$$

For this study, the numerator will be defined as the total number of patients with a diagnosis of primary end points or secondary end points during follow-up period. The denominator will be the total number of all patients at risk in cohorts groups during follow-up period.

Secondly, an incidence density approach calculates time at risk in person-years, measured from first prescription to the end of the observation period. The incidence rate will be reported as per 1,000 person-years of observation as shown in the following formula:

$$\text{Incidence Rate} = (\text{Total new cases during follow up period} / \text{Total person years during follow-up period}) * 1000$$

The numerator will be defined as the total number patients with end points of interest during follow-up period. The denominator will be defined as the sum of person years of patients during the follow up period. For patients who have incidence of primary or secondary end points, person time will equal the sum of days from their first prescription of treatment (index prescription) until the date of the incident condition (diagnosis of primary or secondary end points). For patients who do not experience an incidence of primary or secondary end points, person time will equal the sum of days from their first prescription of treatment (index prescription) to the last visit date or completion of 5 years follow up at which all patients will be censored, whichever occurs first.

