In the determination of person years, the date of first prescription of treatment will be used as a surrogate for time of first exposure to treatment, since the date when the patient had their first treatment for osteoporosis may not be consistently ascertainable. The same definition of person-time ('ever' exposed approach accounting for all person-times of exposure) will be used for all the study endpoints given that they are all chronic diseases or malignancies with potentially long latency periods. If no primary end point occurs during the follow-up period, the duration will be calculated from the start of treatment date to the last patient visit or the end of study period, whichever comes first.

Both methods of calculating incidence rates will be used and the number of patients for whom the date of first treatment for osteoporosis could not be ascertained will be provided as part of the sensitivity analysis of the incidence density approach.

Stratifications by risks of interest (e.g. age, BMI, or selected medical history) will be performed for each outcome and descriptive summaries will be reported. For example, VTE incidence will be stratified according to age as well as by BMI. Other stratifications by medical co-morbidities and other variables of interest will also be performed as appropriate.

Given the rarity of certain malignancies in this population, the incidence rates observed in this study may be small and imprecise. To better characterize the rates obtained in this study, an additional analysis using external reference data for the malignancies will be conducted, i.e. a standardized incidence ratio (SIR). The observed frequency of malignancies in all three treatment groups will be compared with the expected frequency calculated from an age and gender matched population-based reference group (e.g., GloboCan). This SIR of observed versus expected events and 95% confidence interval, will be reported.

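### The age-stratified 1:6 bisphosphonate sample keeps the bisphosphonate cohort's own age mix, so it does not balance age against bazedoxifene and leaves the crude VTE comparison open to age confounding

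*SAP*

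**What the plan says.** SAP 5.4 reports that "there are 1,823 patients in the bazedoxifene group and 82,041 patients in the bisphosphonate group" and gives the reason for sampling: "To limit the number of patients in the bisphosphonate group, an age stratified random subgroup will be selected". Citing the protocol's sample size section, it says that "the 1,823 bazedoxifene subjects will be adequately matched by a ratio of 1:6 bisphosphonate subjects", which gives a target of 10,938.

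The age bands are 45-49, 50-59, 60-69 and 70 or over. The allocation starts from this statement: "In the bisphosphonate group, the percentage of subjects in each of these age groups is 1.4%, 13.7%, 28.7%, and 56.2% respectively". It continues: "To maintain the same proportion of subjects in each age group for the bisphosphonate subgroup, there will be" 153, 1,499, 3,139 and 6,147 women selected at random from the four bands.

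SAP 8.2.5 makes this sample part of population (a) for the VTE comparison: "Full BZA full raloxifene, random age stratified bisphosphonate subgroup". On method, SAP 8.1.2 states: "The cumulative incidence approach will be used as the primary analysis". The formula is new cases divided by persons at risk, with no age term. The same section also plans that "VTE incidence will be stratified according to age as well as by BMI", reported as descriptive summaries.

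SAP 4.2 and 8.2.2 use the Cox hazard ratio to compare event rates. SAP 8.1.4 lists age among the factors to consider, takes variables into the multivariate model at a univariate p-value of 0.20 or less, and forces in only the treatment indicators. SAP 8.2.4 calls the time-to-event analysis secondary.

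**The concern.** A comparator sample stratified by age would normally be expected to bring the comparator's ages into line with those of the exposed group. This one cannot, because the band targets come from the bisphosphonate cohort alone. Fixing the band counts in proportion to the cohort's own bands gives, in expectation, the age mix of a simple random sample of that cohort.

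What is at stake is the unadjusted VTE result. If the bazedoxifene women are younger than a comparator with 56.2% aged 70 or over, and VTE risk rises with age, the crude ratio is pulled down and could mask an excess that this safety study exists to characterise. If they are older, it is pushed up. Protocol Table 3 is built around underlying rate ratios of 1, 1.5 and 2, so a distortion of a few tenths matters.

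**Working it through.** **1. Reproduce the plan's figures (SAP 5.4).**
- Total: 1,823 × 6 = 10,938.
- Bands: 10,938 × (0.014, 0.137, 0.287, 0.562) = 153.1, 1,498.5, 3,139.2, 6,147.2. These round to the stated 153, 1,499, 3,139 and 6,147, which sum to 10,938. The arithmetic is correct.

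**2. Sampling fraction by band.**
- Women available: 82,041 × share = about 1,149, 11,240, 23,546 and 46,107.
- Stated count / available = 0.1332, 0.1334, 0.1333, 0.1333. Overall: 10,938 / 82,041 = 0.1333.
- The fraction is uniform, so the sample has the full cohort's age mix. It neither removes nor adds an age difference from the bazedoxifene women.

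**3. What an age difference would do to the crude ratio.** The documents give neither the bazedoxifene age mix nor VTE rates by age, so everything in this step except the bisphosphonate shares is assumed.
- Factor = Σ(bazedoxifene share × r) / Σ(bisphosphonate share × r), with r = k^((age − 65)/10), representative ages 47, 55, 65 and 76, and k = 1.5 or 2.0 per decade.
- k = 1.5: r = 0.482, 0.667, 1, 1.562. Denominator = 0.0067 + 0.0913 + 0.2870 + 0.8779 = 1.263.
- k = 2.0: r = 0.287, 0.500, 1, 2.144. Denominator = 0.0040 + 0.0685 + 0.2870 + 1.2047 = 1.564.

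| Assumed bazedoxifene mix, % (45-49 / 50-59 / 60-69 / ≥70) | k = 1.5 | k = 2.0 |
|---|---|---|
| Same as bisphosphonate | 1.00 | 1.00 |
| Moderately younger, 3/25/37/35 | 1.098/1.263 = 0.87 | 1.254/1.564 = 0.80 |
| Much younger, 5/40/35/20 | 0.953/1.263 = 0.75 | 0.993/1.564 = 0.63 |
| Older, 1/8/25/66 | 1.339/1.263 = 1.06 | 1.708/1.564 = 1.09 |

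A true ratio of 1.5 would appear as about 1.30 or 1.20 in the moderately younger case, 1.13 or 0.95 in the much younger case, and 1.59 or 1.64 in the older case.

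**4. Can the sample be drawn to the bazedoxifene mix at 1:6?** Available women / 6 = about 191, 1,873, 3,924 and 7,685 bazedoxifene women by band. The much younger mix, the most demanding of these in the two youngest bands, needs 10,938 × (0.05, 0.40, 0.35, 0.20) = 547, 4,375, 3,828 and 2,188 bisphosphonate women. All are well inside the numbers available.

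**5. Cost in precision.** Information for an age-stratified log rate ratio is approximately Σ e₁e₀/(e₁ + e₀), where e₁ and e₀ are the expected events in the two groups in each band. Redrawing to the bazedoxifene mix changes this by about −2% to +6% across the assumed mixes, both values of k, and true ratios from 1 to 2.

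**The case against.** The strongest reply is that the SAP never promises age matching. Its stated aim is to limit numbers, and the word matched is tied to the 1:6 ratio. Proportional sampling does what that aim requires, keeps the sample representative of bisphosphonate users, and gives in expectation the same crude comparison as all 82,041 women. That stands. A reader might infer that the SAP makes a false claim of age matching, or that the sampling itself introduces bias. The text supports neither.

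A reader might also infer that the crude comparison is confounded by age. That is not shown. It needs the bazedoxifene mix to differ and VTE risk to vary with age, and the documents supply figures for neither. The only remark that a cohort may be younger (protocol section 10) concerns raloxifene relative to bazedoxifene.

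Third, age is handled elsewhere. Age is described by cohort, VTE incidence is stratified by age, and the Cox hazard ratio is the formal comparison. SAP 8.1.4 intends the model to control imbalances in risk factors, and SAP 8.2.5 refers to covariates associated with both outcome and exposure. Age would also probably pass the entry screen where it matters. Using 1.74 per 1,000 patient-years and 15% annual loss (protocol 7.1), mean follow-up over 5 years is (1 − 0.85⁵)/(−ln 0.85) = 3.42 years, so 12,761 women would give about 12,761 × 3.42 × 0.00174 = 76 VTEs. With the assumed age gradients, the chance that age passes p ≤ 0.20 is then roughly 87-94% at 1.5-fold per decade and about 99% at 2-fold.

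This limits the concern without removing it. Entry of age is likely but not guaranteed, the age-stratified rates are descriptive with no pooled or standardised ratio, and the analysis that could adjust for age is labelled secondary while an unadjusted incidence is labelled primary.

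**Conclusion.** The concern holds as a limited, inexpensive improvement. It is certain, from SAP 5.4 alone, that the sample takes a uniform 13.3% of each band and that the age stratification does nothing for comparability with the bazedoxifene women. It follows that the crude cumulative-incidence comparison and the univariate hazard ratio stay open to age confounding.

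The size is unknown. Under the assumed mixes and a 1.5- to 2-fold rise in VTE per decade, the crude ratio is multiplied by about 0.63 to 1.09, and by 1.0 if the mixes are equal. The low end rests on an extreme assumption (20% of bazedoxifene women aged 70 or over, against 56.2%). The age-adjusted Cox result is much less exposed, provided age enters the model.

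**What to change.** In SAP 5.4, replace the bisphosphonate proportions with the age distribution of the bazedoxifene women: within each age band, draw six bisphosphonate women at random per bazedoxifene woman. The total stays at 10,938. If the full bisphosphonate cohort is analysed instead, age-standardise the crude incidence and the ratio to the bazedoxifene age distribution. Unless one of these is done, state that matched refers only to the numerical ratio. In any case, report the bazedoxifene age mix next to the bisphosphonate one.

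The cost is a change of SAP wording and of the band targets in the sampling program, with almost no change in information. There are two limits. The sampled crude bisphosphonate rate would no longer describe all bisphosphonate users, so the full-cohort rate should be reported alongside. Four bands also leave any age difference within the open-ended group aged 70 or over. Forcing age into the multivariate Cox model is a separate, compatible change that would remove the dependence on the p ≤ 0.20 screen.
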